#### **Biochemical Profiling:**

A part of the serum samples will be used to analyze hepatokine, cytokine, adiponectin, leptin, HbA1c, androgen (testosterone and DHEAS) levels along with LFT, CRP, Insulin, HOMA-IR, fasting glucose and lipid profile.

#### Lipidomic Analysis:

*Lipid extraction:* 0.5 ml pre-chilled MeOH/chloroform (2:1) mixture containing internal standards will be added to the tube containing 100  $\mu$ L frozen serum sample. The mixture will be vortexed for 30 sec. 0.4 ml of ice-cold water will be added to the mixture to enable phase-separation. Sample will be mixed vigorously at room temperature for 10 minutes and centrifuged 20 mins at 14 krpm at 4°C. The lower organic layer will be collected in glass tube and dried under nitrogen flow. The sample will be reconstituted in 100 $\mu$ L internal chloroform/MeOH (1:1) containing internal standards for MS quality control. For specific lipid classes such as phospholipids and oxolipins, sample clean-up and enrichment will be performed using 96-well Oasis HLB solid-phase extraction plates.

Analysis of lipid composition: Lipids comprise of diverse class of molecules with each class consisting several distinct members that vary widely in their abundance and chemical properties. This makes analysis of lipid composition quite a challenging task. However, advances in chromatography, particularly, introduction of ultraperformance liquid chromatography coupled with high-resolution mass spectrometry has enabled significant coverage of the lipidome. In this study ultraperformance liquid chromatography (UPLC; Acquity UPLC, Waters Corp.) coupled with electrospray ionization mass spectrometry (ESIMS; Xevo G2 qTOF MS, Waters Corp) will be used for analysis of complex lipids. However, fatty acids and sterol-related compounds are not easily ionizable in ESIMS. Therefore, gas chromatography coupled with mass spectrometry (GC-MS) will be used to analyze composition of fatty acid and sterol-related compounds.

(A) UPLC-ESIMS Analysis: Lipid extract will be diluted in acetonitrile/isopropanol/water (1:2:1) and and transferred to glass sample vials for ESIMS analysis. Lipids will be separated on a reverse phase (C18) column prior to introduction to ESIMS. Samples will be run in a randomized manner with intermittent injection of pooled and authentic standard mixture samples for quality control.

Chromatograms will be aligned, deconvoluted and binned to extract features. Identification of features will be performed through analysis of MS/MS fragmentation pattern and comparison with authentic standards (whenever available).

(B) GC-MS Analysis: Lipid extract will be mixed with internal standards for derivatization and extraction. Methyl esters of fatty acids will be prepared via esterification using Methanolic HCl. Methyl esters will be extracted using hexane, evaporated to dryness under nitrogen and reconstituted in hexane containing internal standard for GC-MS quality control. For steroids, samples will be derivatized using MSTFA containing 0.5% TMSI. Compounds will be separated on a HP5-MS or DB5 column with helium as the carrier gas in gas chromatograph (Agilent 7890B) and ionized through electron impact ionization and analyzed using a single quad mass spectrometer (Agilent 5977B). Total ion chromatogram will be aligned and deconvoluted to extract features and identify changes in composition. Identification of compounds of interest will be through analysis of fragmentation pattern, matching against NIST Library and comparison with authentic standards (whenever available).

**Data mining:** Data redundancy often leads to model over fitting in multivariate analysis. Such redundancy may arise due to in-source fragmentation and adducts in mass spectrometry. Inter-feature correlation will be examined across samples to identify covariant features. In case, they appear within same retention time window, raw chromatograms will be analyzed to identify putative adducts or fragments. They will be excluded from further analysis. Principal component analysis (PCA) will be used to examine any segregation of lipidomic signature and their correlation with phenotypes of interest (PCOS and sub-features of PCOS). Supervised analysis (PLS-DA and OPLS-DA) will be used to identify features that could predict phenotypes of interest. Iterative 'leave-one-out' cross validation (number of iteration

> 20% of the size of the nested cohort) will be used to validate the model. For univariate analysis non-parametric statistical test assuming unequal variance will be employed given the limited sample size. Unpaired Mann-Whitney 'U' test with Bonferroni correction for multiple testing will be used identify lipids (say, set 'A') that shows significant difference in abundance between controls and cases at a given time point. Paired Mann-Whitney test with Bonferroni correction will be used to identify lipids (say, set 'B') that shows significant change in abundance with disease onset in naive subjects. Molecules (say, set 'C') that shows similar pattern of change with time in all three groups, i.e., subjects that present PCOS at beginning, those that develop PCOS during the study and those who never develop PCOS, will be excluded from further analysis to identify putative biomarkers. Rest of the molecules that are common in both sets (A and B) and shows similar pattern of change associated with disease status will be tested as potential biomarkers related to PCOS. In addition, the correlation between lipidomic signatures and non-PCOS clinical or biochemical parameters (such as, body weight, BMI, WC, body fat, fasting glucose, insulin concentration, liver fibrosis score, etc) will be examined. Receiver operating characteristic (ROC) analysis will be performed to examine the sensitivity and specificity of these candidate biomarkers for PCOS diagnosis. In case, there are significant number of new cases of PCOS in both 2nd and 3rd year, cases up to 2nd year will be used to identify consensus lipidomic changes associated with PCOS as described above. Rest of the cases will be used to prospectively validate PCOS markers through ROC analysis. In addition, the ability of baseline abundance of such molecules to predict PCOS incidence at a later time point will be examined using ROC analysis. This would help to identify a multivariate signature that could help to predict PCOS risk in naive subjects.

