#### **Epidemiology:**

Data on incidence of PCOS is hugely influenced by the definition of PCOS followed in the respective study. PCOS incidence has been reported to vary from 2.2-26% worldwide (1-5). In India, only a handful of epidemiological studies have been reported on PCOS. The following table summarizes results of those studies. Table 1: Summary of Epidemiological Studies on PCOS in India

 Study Design	Location	Sample size	Age range	Incidence (%)	PCOS definition	Non- obese PCOS (%)	Reference
Cross- sectional	Mumbai	778	15-24	22.5 10.7	Rotterdam NIH	71.8%	Joshi B et al Indian Journal of Endocrinology and Metabolism / May-Jun

							2014 / Vol 18   Issue 3
Cross- sectional	Kanchipuram/Chennai	1068	18-24	6	Rotterdam	62%	Bharathi, RV Middle East Fertility Society Journal 22 (2017) 313– 316
Cross- sectional	Bangalore	460	18-45	9.13	Rotterdam	-	R Nidhi et al J Pediatr Adolesc Gynecol 24 (2011) 223e227
Cross- sectional	Dehradun	170	16- 30+	41	NIH	14%	Choudhary A et al. Int J Reprod Contracept Obstet Gynecol. 2017 Nov;6(11):4971-4975
Cross- sectional	Bhopal	500	17-24	8.4	Rotterdam	17%	Gupta M et al. Int J Community Med Public Health. 2018 Jan;5(1):95-100
Cross- sectional	Sevagram	200	15-34	50	Rotterdam	-	Chhabra S J Obstet Gynaecol. 2010 Jan;30(1):41-5.
Cross- sectional	Vellore	126	12-19	18	Rotterdam	-	Balaji, S et al Biomed Res Int. 2015;2015:158951.

As can be seen in the table, PCOS incidence varied widely from 6-50% among different studies. This calls for multi-centre studies involving larger sample size and uniform diagnostic criteria. Few studies (Bharathi, RV et al and Balaji S et al) have indicated higher incidence of PCOS in urban women. While stress and other life-style

related factors may contribute to a higher abundance as suggested in these articles, underreporting in rural set up due to stigma involved with consequences of PCOS may also contribute to this difference. One of the striking features of PCOS in India is that a significant percentage of PCOS patients are non-obese at diagnosis. However, it should be noted that all these studies stratify subjects based on BMI and/or waist circumference. None of them analyzed the total body fat using technologies such as dual energy X-ray absorptiometry (DEXA), which truly represents the adiposity of the subject.

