#### **Study population**

Freshers admitted in MBBS course at IPGME&R and SSKM hospital. We aim to recruit 200 subjects.

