#### **Overview of the Workflow:**

Approximately 200 young adult subjects will be enrolled and examined for PCOS incidence as per Rotterdam criteria in addition to comprehensive physio-clinical, radiological and biochemical evaluation. This exercise will be repeated for all subjects every year.

**Figure 1:** Schematic representation of overall plan of work for identification of early markers of PCOS using serum lipidomics.

Serum samples collected during this exercise will be subjected to lipidomic analysis using Ultra-performance liquid chromatography (UPLC)-electrospray ionization mass spectrometry (ESI-MS) as well as gas chromatography coupled with mass spectrometry (GC-MS). These data will be combined and mined using multivariate statistical analysis to identify features of interest. This will be further subjected to rigorous statistical analysis for robustness of association of signatures with PCOS.

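### The leave-one-out validation of the PLS-DA/OPLS-DA models has an iteration floor of just over 20% of the nested cohort, which permits an incomplete run, and the unit left out is not stated

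*Protocol*

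**What the plan says.** All of this is in section 1.4 of the protocol; no statistical analysis plan was available.

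- **Models.** The Data mining paragraph under Lipidomic Analysis states: "Supervised analysis (PLS-DA and OPLS-DA) will be used to identify features that could predict phenotypes of interest".
- **Validation.** The same paragraph continues: "Iterative 'leave-one-out' cross validation (number of iteration". After a greater-than sign, the sentence ends: "20% of the size of the nested cohort) will be used to validate the model". The figure is therefore a minimum, and no upper value is given.
- **Cohort.** Under Study population: "We aim to recruit 200 subjects". The size of the nested cohort is not given separately.
- **Repeat sampling.** Under Overview of the Workflow, after enrolment and evaluation: "This exercise will be repeated for all subjects every year". The work plan places serum collection at months 1-3, 13-15 and 25-27, so a woman can contribute up to three samples.
- **Frequency of PCOS.** No rate is assumed for this cohort. The Epidemiology section says of earlier Indian studies: "PCOS incidence varied widely from 6-50% among different studies".

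**The concern.** Leave-one-out predicts each unit once from a model fitted to all the others, so the number of iterations equals the number of units. A minimum of about one fifth of the cohort is a different procedure. Reading an iteration as a repeat of the whole run does not help, because leave-one-out on fixed data with a fixed model gives the same answer each time.

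Two things are then left open. The first is which women are predicted: the analyst could stop at any point past the floor, and nothing says how those tested are chosen. The second is what the one left out consists of, a woman or a serum sample. This matters because women are sampled yearly.

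At stake is the only unconditional internal check on the multivariate models. If it rests on a few cases, the stated sensitivity of a predictive lipid signature says little. The rule stands in the protocol itself, so an analysis plan that followed it to the letter could still run the partial version.

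**Working it through.** The protocol derives no sample size, power or expected case number, so there is no figure of its own to reproduce. The check is what the floor allows.

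**Inputs**
- N = 200 women (Study population). Taking this as the nested cohort is an assumption.
- Floor: more than 20% of the cohort (Data mining).
- Case share p (assumed for this cohort): the Rotterdam studies in Table 1 with ages between 12 and 24 give 6%, 8.4%, 18% and 22.5%. The highest rate in the table is 50%.

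**Step 1: smallest number of iterations that complies**

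floor(0.20 × N) + 1 = floor(40) + 1 = 41, or 20.5% of 200. Women who need never be predicted: 200 − 41 = 159.

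**Step 2: cases held out at the floor and in a complete run**

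Expected cases at the floor = 41 × K/200, where K = 200p rounded. The 95% range is hypergeometric and assumes that the 41 women are drawn at random, which the protocol does not say.

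| Rate | Cases in 200 (K) | Expected among 41 | 95% range |
|---|---|---|---|
| 6% | 12 | 2.5 | 0 to 5 |
| 8.4% | 17 | 3.5 | 1 to 7 |
| 18% | 36 | 7.4 | 3 to 12 |
| 22.5% | 45 | 9.2 | 5 to 14 |
| 50% | 100 | 20.5 | 15 to 26 |

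At 6%, the chance that the 41 women include no case at all is 5.8%.

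**Step 3: precision of sensitivity** (exact Clopper-Pearson 95% intervals, true sensitivity near 80%, rate 22.5%)
- Floor: 7/9 correct gives 0.40 to 0.97.
- Complete run: 36/45 correct gives 0.65 to 0.90.

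**Step 4: if the nested cohort is cases plus one control each**
- 12 cases and 12 controls: floor(0.20 × 24) + 1 = 5 iterations, with 5 × 12/24 = 2.5 expected cases.
- 45 cases and 45 controls: floor(0.20 × 90) + 1 = 19 iterations, with 19 × 45/90 = 9.5 expected cases.

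The expected number of held-out cases hardly changes, because the floor scales with the cohort.

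**Step 5: the unit left out**

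Three visits for 200 women give up to 600 samples. If visits were pooled and one sample left out at a time, up to two samples from the same woman would stay in the training set. The protocol does not say whether the supervised models use one visit or several, so no size is put on this.

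**The case against.** **The floor is only a minimum.** More than 20% also allows all N iterations, so the models could, rather than would, be validated on few cases. This stands. The defect is that the rule permits the partial run.

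**The case counts rest on assumptions.** The nested cohort may not be all 200 recruits, cited rates reach 50%, and section 14 (Challenges & constraints) plans to recruit from neighbouring hospitals if PCOS cases at the start are too few. All of this stands and makes the lower counts less certain. Even at 50%, though, about 20 of 100 cases would be tested.

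**A reader might infer that single samples are left out and that the results will leak.** The documents do not support this. The unit is unnamed, and counting iterations against a cohort points, if anywhere, to women. The univariate case-control test is made at a single time point. The workflow sentence "These data will be combined and mined using multivariate statistical analysis to identify features of interest" directly follows the two mass spectrometry platforms and most naturally means combining those, not visits. The warning "Data redundancy often leads to model over fitting in multivariate analysis" concerns adducts and in-source fragments. Leakage would need both pooling of visits and sample-level omission, and neither is stated.

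**A reader might also infer that lipids are selected outside the validation loop.** The filter described before the supervised models removes adducts and fragments and uses no outcome labels. Handling within folds is commonly left to an analysis plan. It belongs in the remedy, not among the errors.

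**Other validation is planned.** Data mining foresees ROC validation in later cases, and sections 14 and 19 mention independent cohorts. The first depends on an undefined sufficiency of new cases in both the second and third years. The independent cohorts come after markers are found. These checks limit the consequence but do not replace the cross-validation of the models.

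**The project is described as exploratory** (section 18). This stands as a reason to rate the point below must-fix.

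**Conclusion.** The point holds in a limited form. The protocol names leave-one-out and then fixes an iteration rule that contradicts it, with no rule for who is tested. With 200 women in the nested cohort, one fifth of them would satisfy the text. At cited rates of 6% to 22.5%, about 2.5 to 9 cases would then carry the estimate of sensitivity instead of 12 to 45. These counts depend on the assumed cohort size and PCOS rate; the contradiction in the rule does not.

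The unstated unit is a gap to close, not a demonstrated error. Severity: should-fix.

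**What to change.** In the Data mining paragraph:

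- Delete the iteration rule of more than 20%.
- State that every woman in the nested cohort is left out once, together with all her samples. Woman-level k-fold cross-validation covering all women would serve equally well.
- State that any lipid selection based on the outcome, and any tuning, is repeated inside each fold.
- Give the definition of the nested cohort, so that the number of iterations follows from it.

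This takes a few sentences and some computing time, with no extra participants or assays. The reported accuracy may come out lower.

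### The univariate rule asks for a rank test that allows unequal variance, but the Mann-Whitney U test named for set A lacks that property when a significant result is read as a difference in abundance

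*Protocol*

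**What the plan says.** All of this stands in the protocol, section 1.4, under Lipidomic Analysis, in the Data mining paragraph.

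- The rule for the univariate analysis: a "non-parametric statistical test assuming unequal variance will be employed given the limited sample size".
- The test for set A, in the next sentence: "Unpaired Mann-Whitney 'U' test with Bonferroni correction for multiple testing will be used identify lipids".
- What membership of set A is taken to mean: a lipid that "shows significant difference in abundance between controls and cases at a given time point".

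On group sizes, Study population says "We aim to recruit 200 subjects", and Sampling methods enrols all consenting adults and classifies them as PCOS or non-PCOS afterwards. No case-to-control ratio is given. The Epidemiology section reports that "PCOS incidence varied widely from 6-50% among different studies". The protocol names no unequal-variance version of the rank test, and no other section reconciles the two sentences.

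**The concern.** The p-value of the Mann-Whitney test uses a null variance that is correct only if cases and controls have the same distribution, including the same spread. The rule sentence says that equal spread is not to be assumed. The test named in the next sentence therefore does not have the property that the rule asks for.

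This matters because set A is read as a statement about level. Suppose a lipid has the same median in cases and controls but a different spread. If the groups are unequal, the test does not hold its nominal level for the question of whether abundance is shifted. When the smaller group is the more variable, too many such lipids enter set A. When it is the less variable, the test is too strict and real shifts are harder to detect. A lipid lost that way cannot become a candidate marker, because candidates must be in both set A and set B.

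**Working it through.** The protocol gives no alpha, number of lipids, SD or sample-size calculation, so there is no figure of its own to reproduce. The check computes the true size of the named test under stated assumptions.

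**Inputs from the protocol**

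- Total of 200 subjects (Study population).
- The table of Indian studies in Epidemiology has six Rotterdam figures: 22.5, 6, 9.13, 8.4, 50 and 18%. Five of the six lie between 6 and 22.5%. Of 200, 6% is 12 cases, 22.5% is 45 and 50% is 100.

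**Assumptions**

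- Log-abundance is normal with equal medians in the two groups.
- The case-to-control SD ratio r is 0.5, 1, 1.5 or 2.
- The test is two-sided at nominal 5%.
- For the far tail, 500 lipids are assumed, giving 0.05/500 = 0.0001 per lipid.

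**Formula.** Let n1 be cases, n2 controls and N = n1 + n2. The test uses the null variance n1·n2·(N+1)/12. With equal medians and SD ratio r, the true variance of U is

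n1·n2·[1/4 + (n2−1)·a + (n1−1)·b], with a = arcsin(r²/(1+r²))/(2π) and b = arcsin(1/(1+r²))/(2π).

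Write k for true variance divided by null variance. The true size at nominal 5% is then about 2·[1 − Φ(1.960/√k)].

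**Check at r = 1.** Here a = b = 1/12, and 1/4 + 198/12 = 16.75 = 201/12. So k = 1 and the size is 5%, as it should be.

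**40 cases v 160 controls** (null value 201/12 = 16.75):

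- r = 1.5: 0.25 + 159×0.12170 + 39×0.04978 = 21.54; k = 1.286; size 8.4%.
- r = 2: 0.25 + 159×0.14758 + 39×0.03205 = 24.97; k = 1.490; size 10.8%.
- r = 0.5: 0.25 + 159×0.03205 + 39×0.14758 = 11.10; k = 0.663; size 1.6%.

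**Other splits of 200, same formula, size at nominal 5%**

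| Cases v controls | r = 0.5 | r = 1 | r = 1.5 | r = 2 |
|---|---|---|---|---|
| 12 v 188 | 0.4% | 5.0% | 9.8% | 13.1% |
| 40 v 160 | 1.6% | 5.0% | 8.4% | 10.8% |
| 45 v 155 | 1.9% | 5.0% | 8.1% | 10.4% |
| 100 v 100 | 5.9% | 5.0% | 5.3% | 5.9% |

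Simulations with 200,000 or more replicates per setting agree with these values to within about 0.2 percentage points.

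**Far tail.** The relative error grows where Bonferroni operates. In simulations of 40 v 160 at nominal 0.01%, the test rejects about 0.05% of the time at r = 1.5 and about 0.11 to 0.14% at r = 2.

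**Does Brunner-Munzel do better?** With its usual t approximation, its size at nominal 5% was 5.0 to 5.4% at every split tried. At nominal 0.0005 it was 0.0005 to 0.0009 with 36 or more cases, but 0.0009 to 0.0024 with 12 to 18 cases. One simulation of the studentised permutation form at nominal 0.0005, with r = 1.5 and 2, gave 0.0010 and 0.0012 for 12 v 188, and 0.0008 and 0.0009 for 20 v 180. For comparison, Mann-Whitney at 12 v 188 gave 0.0024 and about 0.006. At nominal 0.0001 the permutation form was about 2 to 4 times nominal, with more simulation noise. It improves on Mann-Whitney but does not fully hold its level in the far tail with so few cases.

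**The case against.** The strongest reply is that the unequal-variance clause is only a loose reason for going non-parametric, and that Mann-Whitney with Bonferroni is an ordinary choice. Several parts of that reply stand.

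- A reader might infer that the Bonferroni error rate of set A is simply wrong. The documents do not support that. For a lipid whose whole distribution is unrelated to PCOS, the test keeps its level. The departure concerns lipids that differ in spread but not in level, and it arises because the plan reads significance as a difference in abundance.
- The rank test is unaffected by monotone transformation. Unequal variance on the raw scale that vanishes on the log scale does no harm.
- A reader might take the heterogeneity of PCOS described under Definition, Criteria for Diagnosis and Their Limitations as evidence of wider lipid spread in cases. That text concerns the types of symptoms that patients present. It says nothing about lipid variability.
- Unequal groups are likely but not fixed. Challenges & constraints provides for recruiting further subjects from neighbouring hospitals if baseline cases are too few, no matching ratio is set, and new cases may be added in later years.
- A reader might carry the inflation over to the final marker list. Candidates must also pass the Bonferroni-corrected paired comparison of set B, survive the exclusion of set C and show a consistent pattern, followed by ROC analysis and later validation. The effect on that list has not been computed. The project also describes itself as exploratory.

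What the reply does not remove is the mismatch. Mann-Whitney is valid under identical distributions, but then the spreads are equal, and the rule sentence declines to assume that. Nor does set B recover a lipid that an over-strict test has kept out of set A.

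**Conclusion.** The point holds as an internal inconsistency with a conditional consequence. Two adjacent sentences specify a property and then a test without it, given how set A is interpreted. That much needs no assumption.

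The size depends on assumptions. With 12 to 45 cases of 200, the true level at nominal 5% runs from about 8 to 13% when case SD is 1.5 to 2 times control SD, and from 0.4 to 1.9% when it is half. With equal spread the error is negligible, and with 100 per group the level is 5.3 to 5.9%. The SD ratios, the normal log-abundance and the lipid count are not in the protocol, so these figures are illustrative.

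The evidence does not show that set A will be full of false findings, or that the final marker list has these error rates.

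**What to change.** In the Data mining paragraph, choose one of two routes.

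1. **Keep the unequal-variance requirement.** For set A, replace the unpaired Mann-Whitney U test with a rank test that allows unequal spread: Brunner-Munzel, with studentised permutation p-values when cases are few. Keep the Bonferroni correction. Note in the text that with about 12 to 20 cases this reduces far-tail inflation but may not remove it. Welch's t-test on log-abundance is an alternative only if the non-parametric requirement is dropped. Under normal log-abundance and with at least 20 cases it held 5.0% at nominal 5%, and 0.009 to 0.015% at nominal 0.01%.
2. **Keep Mann-Whitney.** Delete the unequal-variance clause and state that set A tests equality of the two distributions, so that membership does not by itself show a shift in abundance.

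Either route changes a sentence or two. The first also costs a different function call, more computing time for the permutations, and slightly lower power where the spreads are in fact equal. The second costs nothing in computing but weakens what set A can be said to show.

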#### Lipidomic analysis in PCOS:

Sun et al first reported changes in plasma lipid profile of PCOS patients using NMR in 2012(2). 34 PCOS (average age 26.9) and 36 controls (average age 27.2) were analyzed in the cross sectional study. Decrease in glycerophosphocholine/choline was observed in the PCOS patients. However, since NMR was, identity of these lipids remained elusive to the study. In 2015, Houla et al (7) reported use of LC-MS, which is much more informative on the identity of lipids, to analyze lipidomic changes plasma samples of PCOS patients. In the cross sectional study involving women aged 18-40 years, 40 PCOS and 40 non-PCOS controls were recruited. Significant changes in phospholipids, sphingomyelins, diand tri- acylglycerols were observed. However, the average BMI of PCOS patients (29.5) were significantly higher than that of controls (25.4), which calls for a more guarded approach in associating changes in lipid composition to PCOS alone. Moran, L et al (8) examined correlation between features of PCOS and lipidomic changes in a cross-sectional study involving women with (n = 64) or without PCOS (n = 92) aged 18-45. The changes in lipid composition correlated most with central obesity and free androgen index. But even in this study both body weight and BMI of PCOS patients were significantly higher than control. Li S et al (9) reported analysis of the changes in lipids including polyunsaturated fatty acid metabolites in 32 newly diagnosed PCOS patients compared to 34 non-PCOS subjects. Results indicated an opposing effect of insulin and androgen on bioactive metabolites. However, the BMI of the control obese and obese PCOS subjects were significantly different in this study. In 2018, Jove M et al (10) reported analysis of plasma lipidome of 20 lean healthy controls and 14 PCOS patients. Significant downregulation of glycerophospholipids, glycerolipids and sphingolipids were observed suggesting a widespread alteration in lipid metabolism which might influence cellular signalling in PCOS patients.

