While these studies indicated changes in lipid metabolism associated with PCOS, several of them failed to account for confounding factors such as difference in BMI and/or age. In addition, all of these studies were single-time point cross-sectional in nature. Therefore, they do not yield any information on evolution lipidomic signature during pathogenesis. Longitudinal nested case-control study is essential not only to identify any early signature for risk prediction or diagnosis but also to hypothesize on and investigate into the causal relationship between derangement of lipid metabolism and PCOS. It should be noted that neither any longitudinal nor any cross-sectional sectional lipidomic analysis has ever been reported in Indian PCOS patients.

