#### **1.4** Research design, methodology, timelines and milestones (up to ten pages):

#### Study Design:

Longitudinal nested case-control, hospital-based.

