#### Sampling methods

All voluntarily consenting adults will be enrolled and clinically evaluated as per Rotterdam criteria to designate them as

PCOS or non-PCOS cases.

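### Adiposity plays no part in selecting or testing the lipid markers, and the A-and-B rule does not remove fat gain that accompanies PCOS onset

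*Protocol*

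**What the plan says.** **Design.** The study is "Longitudinal nested case-control, hospital-based" (Protocol, Study Design), and the Study population section states "We aim to recruit 200 subjects". Under Sampling methods, "All voluntarily consenting adults will be enrolled and clinically evaluated as per Rotterdam criteria to designate them as" PCOS or non-PCOS. No matching factor or rule for sampling controls is given.

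**Selection (Lipidomic Analysis, Data mining).**
- Set A: "Unpaired Mann-Whitney 'U' test with Bonferroni correction for multiple testing will be used identify lipids" "that shows significant difference in abundance between controls and cases at a given time point".
- Set B: lipids that change with disease onset in initially naive women, by a paired test with Bonferroni correction.
- Set C: molecules with a similar time pattern in women with PCOS at entry, women who develop it and women who never do. These are dropped.
- Candidates are molecules in both A and B, with a similar pattern related to disease status, and not in C.

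PLS-DA and OPLS-DA are used to find predictive features. ROC analysis then assesses the candidates for diagnosis and for prediction from baseline. No adiposity covariate, stratum or comparator is named in any of these steps.

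**Adiposity.** Clinical assessment records BMI, waist circumference and body fat. In the analysis they enter only as an addition, when "the correlation between lipidomic signatures and non-PCOS clinical or biochemical parameters" will be examined. No consequence for selection is attached to that.

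**Background (Lipidomic analysis in PCOS).** Of earlier studies the protocol says that "several of them failed to account for confounding factors such as difference in BMI and/or age". One example it gives is a mean BMI of 29.5 in cases against 25.4 in controls.

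**The concern.** The protocol accepts that obesity and PCOS are associated, and reports that in one cited study lipid changes correlated most with central obesity and free androgen index. If cases in this cohort are fatter than controls, a lipid that only follows body fat will differ between them. Bonferroni correction limits chance findings; it does not remove a systematic difference. The group's own preliminary study separated cases and controls by BMI, and the new plan does not.

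At stake is the meaning of the signature. Without an adiposity term, the study cannot say whether a lipid panel tells more about PCOS, or about future PCOS, than a body-fat measurement does. This is not a detail left for a SAP: the protocol itself names the test and the selection rule.

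**Working it through.** The protocol gives no power, effect size or number of lipids for these tests, so there is no stated figure to reproduce. The calculations below show the size of the problem under stated assumptions.

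**Inputs from the protocol.** N = 200. BMI gap 29.5 − 25.4 = 4.1, borrowed from a cited study. PCOS frequency 6% to 50% (Table 1 text); 40 and 20 cases of 200 are 20% and 10%.

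**Assumptions.** BMI SD 5, so the gap is 4.1/5 = 0.82 SD. Lipid-BMI correlation 0.5. No PCOS effect on the lipid. 20 onset women. Within-woman lipid correlation 0.7. Thresholds of 0.0005 and 0.0001 correspond to Bonferroni for 100 and 500 lipids.

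**Step 1: set A.** Lipid difference d = 0.82 × 0.5 = 0.41 SD. Standard error (Mann-Whitney efficiency 3/π) = √(1/n1 + 1/n0) × √(π/3). The chance of being flagged is Φ(d/SE − z), with z the two-sided critical value; the opposite tail is negligible.

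| Women | SE | d/SE | At 5% | At 0.0001 |
|---|---|---|---|---|
| 40 v 160 | 0.181 | 2.27 | Φ(2.27 − 1.96) = 62% | Φ(2.27 − 3.89) = 5% |
| 20 v 180 | 0.241 | 1.70 | Φ(1.70 − 1.96) = 40% | Φ(1.70 − 3.89) = 1.4% |

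Over a grid of 6% to 50% cases, BMI SD 4 to 6 and correlation 0.2 to 0.5, the rate runs from 7% to 94% at 5%, and from 0.13% to 52% at 0.0005.

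**Step 2: does adjustment work?** In 4,000 simulated studies with 45 cases and 155 controls (correlation 0.5), the null lipid was flagged at 5% in 66% unadjusted and 4.7% after adjustment for BMI. At 0.0005 the figures were 12% and 0.03%.

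**Step 3: the A-and-B rule.** The paired test is read as a signed-rank test, and A and B are treated as independent.
- No mean BMI gain at onset: B passes in the same direction 2.5% of the time at 5%. Jointly 0.025 × 0.62 = 1.6%, about 2%.
- BMI gain of 0.5 SD: mean lipid change 0.5 × 0.5 = 0.25 SD. SD of change √(2 × (1 − 0.7)) = 0.775. Standardised change 0.323. Test statistic 0.323 × √20 × √(3/π) = 1.41. B passes with probability Φ(1.41 − 1.96) = 29%. Jointly 0.29 × 0.62 = 18%; simulation gives about 15%.
- Same gain at 0.0005 each: B Φ(1.41 − 3.48) = 1.9%, A Φ(2.27 − 3.48) = 11%. Jointly 0.2%; simulation gives about 0.15%. The normal approximation is rough this far into the tail with 20 pairs, so read this as 0.2% or less.

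**Step 4: ROC.** The null lipid has AUC Φ(0.41/√2) = 0.61. BMI itself, under the same gap, has AUC Φ(0.82/√2) = 0.72. A lipid with no PCOS information thus appears mildly diagnostic, while a simpler measurement does better. The planned ROC has no comparator that would show this.

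**The case against.** **Set A is not the list of markers.** A reader might infer that lipids tracking body fat will simply be selected as PCOS markers, and take 62% as the false-marker rate. The documents do not support that. The paired set B cancels adiposity that is constant within a woman, and under Bonferroni thresholds the joint rate is small even with weight gain. This objection stands and sets the size of the point. It does not dispose of it: fat gain confined to women at onset passes B, and C removes only patterns shared by all three groups. PLS-DA and OPLS-DA are not described as limited to A-and-B lipids.

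**The BMI gap is borrowed.** It comes from a study of women aged 18 to 40, whereas this cohort is first-year students, and the protocol notes that many Indian patients are non-obese (14% to 71.8% in its table). This stands; the gap here could be much smaller.

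**Prediction may not need independence from adiposity, and adjustment may over-correct.** The work is called exploratory, and the protocol proposes linked insulin, androgen and lipid pathways on which adiposity could lie. It calls for accurate adiposity measurement to investigate the lipid-PCOS connection; a reader might take that as a promise of an adiposity-independent effect, but it does not say so. This is a reason to show both adjusted and unadjusted results, not to omit the adjusted ones. A predictive marker still has to be compared with body fat.

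**Age.** The protocol's criticism covers age too, but recruiting first-year students largely restricts it. The point concerns adiposity.

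**Conclusion.** The point holds in a limited form and should be fixed. The protocol fixes an unmatched, unadjusted case-control test and gives measured adiposity no role in selection, supervised modelling or ROC, despite criticising earlier work for neglecting BMI.

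The A-and-B rule with the set C exclusion is a real safeguard against stable adiposity. What remains is fat gain at onset, and an ROC, including the baseline prediction, that cannot show value beyond adiposity. Under the stated assumptions, passage of a null lipid through A and B at 5% each rises from about 2% to about 15% when onset brings a 0.5 SD BMI gain. At 0.0005 each it is about 0.15%, against practically nil without the gain.

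The gap, SD, correlations, number of lipids and number of onset cases are all assumptions. The adiposity imbalance in this cohort is unknown.

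**What to change.** 1. Keep the rank tests as a screen. Require each candidate's association to persist in a model of log lipid abundance on PCOS status adjusted for measured body fat (or BMI and waist), plus recruiting site if women from neighbouring hospitals are added, as Challenges & constraints allows.
2. Adjust the onset contrast (set B) for the woman's change in body fat over the same interval.
3. Report adjusted and unadjusted results side by side, and state that adiposity may lie partly on the causal path.
4. In the diagnostic, validation and baseline-prediction ROC analyses, report the AUC of body fat or BMI alone and the AUC that the signature adds to it.

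Cost: no new data, since the covariates are already in the clinical assessment. The change is analysis wording, a few degrees of freedom and possibly a shorter candidate list.
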